7. DATA COLLECTION, HANDLING AND RECORD KEEPING

7.1. Study Management Documentation and Logs

Participating clinical sites will maintain a Patient Screening Log and a Subject Enrollment Log. The Patient Screening Log should contain a nonconfidential (coded) listing of potential study patients screened at the clinic for study participation and identify those that were included in the study, those that were not included in the study, and the reasons why patients were not included (excluded). The Subject Enrollment log should identify enrolled study subjects and their assigned Study Subject ID.

7.2. Study Case Report Forms (CRFs)

In addition to instrument electronic report data, study Case Report Forms (CRFs) will be the primary data collection tool for the study and will constitute the original study record. The following study information will be collected using eCRFs/CRFs for each study subject:

- CRF 1** - Consent and Demographics
- CRF 2** - Current Asthma Prescription and Asthma History
- CRF 3** - Other Medical Conditions and Medications
- CRF 4** - Visit #1 - ACQ and Spirometry Results
- CRF 5** - Visit #1 - Vivatmo *pro*TM Results
- CRF 6** - Visit #2 - ACQ and Spirometry Results
- CRF 7** - Visit #2 - Vivatmo *pro*TM Results

Data may be delivered via completion of electronic case report forms (eCRFs) directly into the online study database or by completion and delivery of PDF scans of completed hardcopy case report forms (CRFs). The PI, or designee, at each site must verify the accuracy and completeness of all recorded data by signing and dating all case report forms (eCRFs/CRFs) prior to submitting them. If a manual entry requires change, the correction will be made as follows:

- Draw a single line through the incorrect entry.
- Enter changed/corrected data (“white-out”, erasure, or any form of obliteration of data is not permitted under any circumstances).

Neither the Sponsor nor its designee can interpret a blank answer as “none” or “N/A”; therefore, all fields must be completed. If data are not available, a straight line should be drawn through all applicable fields manually completed forms and unused pages, and dated and initialed to indicate there was no omission.

All supportive documentation must be clearly identified with the Study Subject ID number. Any personal information, including subject name, address, phone number, medical record number, or social security number must be removed or rendered illegible to preserve study subject confidentiality.

All records (e.g., regulatory documents, CRFs, study logs, data sheets) will be sent to the clinical monitor when requested. Unless otherwise instructed, original documents completed at the study site will remain in the Investigational Site File (ISF) while copies will be sent to sponsor, or designee, for the study Trial Master File (TMF).

The PI ensures the accuracy, completeness, legibility, and timeliness of the data reported to Sponsor as well as storage and security of the study files. Study ISF binders and CRF template forms will be provided by the sponsor.

7.3. Vivatmo *pro*TM Instrument Data

The following instrument testing data will be reported to the sponsor or designee:

- Study Visit #1 - Vivatmo *pro*TM Test Results
- Study Visit #2 - Vivatmo *pro*TM Test Results

Instrument test results for each patient visit will be printed at the time of the visit (or immediately after) and stored in study data binder. Electronic exports of Vivatmo *pro*TM study results files will be emailed to the study sponsor or designee for uploading into study database.

Reports for the following will also be printed and stored in the study data binder and delivered electronically to the study Sponsor or designee.

- Vivatmo *pro*TM Initial Set-Up and Installation Information (as needed)
- Vivatmo *pro*TM QC results

7.4. Asthma Control Questionnaire (ACQ) and Spirometry Data

Asthma Control Questionnaire (ACQ) and Spirometry data for each patient visit will be recorded in the designated CRF. These CRFs will include:

- Study Visit #1 - ACQ Responses and Spirometry Testing Result
- Study Visit #2 - ACQ Responses and Spirometry Testing Result

7.5. Record Retention

All records pertaining to this study must be maintained by the PI in a condition suitable for inspection for whichever is the longer of:

- Two (2) years following FDA clearance to market of the investigational product;
- Two (2) years following termination or discontinuance of the entire clinical investigation; or
- Record retention policy of the investigational site and/or IRB/IEC.

7.6. Record Access

The PI and institution will permit study-related monitoring, audits, IRB/IEC review, and regulatory inspection (FDA or other regulatory authority) by providing direct access to study documents.

7.7. Study Training Manual

The study training manual will contain the following:

- Table of Contents
- Study Protocol
- Study Informed Consent Template
- Study Case Report Form Templates (CRFs)
- Screening Log Template
- Enrollment Log Template
- Study Material Accountability Log Template
- Study Deviation Report Template

7.8. The Investigational Site File (ISF)

The Investigational Site File (ISF) a.k.a. “Regulatory Binder” will contain the following:

- IRB approval of Study Protocol
- IRB approved Patient Informed Consent Template
- Completed and Signed Investigator Statement
- Completed and Signed Financial Disclosure Form 3454 or 3455
- Signed Clinical Site Agreement (Clinical Trial Agreement)
- All relevant and significant communications between sponsor, site and IRB, including all electronic and paper communications (e.g., emails, letters)
- Investigator notifications of protocol amendments and addenda
- IRB updates
- PI CV and Licenses
- PI GCP Certifications
- Site Staff Study Training Documentation

7.9. Data Binder

The study data binder will contain the following:

- Original completed Case Report Forms (CRFs)
- Printouts of the Vivatmo pro™ Test Result Data
- Printouts of Vivatmo pro™ Initial Set-Up and Installation Information
- Printouts of Vivatmo pro™ QC results

8. DATA ANALYSIS AND STUDY ENDPOINTS

8.1. Analysis Populations

The Full Analysis Set (FAS) will be defined as all patients intended to receive a FeNO measurement.

The Per Protocol Set will be defined as enrolled subjects without major protocol violations, with inhaled corticosteroid (ICS) treatment, and successfully completing at least one valid FeNO measurement at both Visit #1 and Visit #2 will be evaluated for the primary endpoint.

8.2. Descriptive Statistics

Baseline characteristics, such as demographic, as well as analytical clinical data by visit will be summarized using descriptive statistical methods. Continuous data will be summarized using the mean, the median, standard deviation, and range (minimum and maximum value). Categorical values will be summarized using frequency counts and percentages.

8.3. Analysis of Primary Endpoint

The change of FeNO values will be estimated in ANOVA with baseline values as the covariate and will be reported as percent change together with the 95%-confidence interval.

8.4. Analysis of Secondary Endpoints

The relationship between changes of FeNO-values and clinical assessments (spirometry, ACQ-questionnaire) will be assessed by Spearman's rank correlation.

Repeatability will be estimated together with the 95%-confidence interval as pooled standard deviation (mean of measurement pair < 50 ppb) and CV (mean of measurement pair ≥ 50 ppb), respectively, using the residual variance component resulting from a random effects ANOVA (as used in CLSI EP05 guideline) with patient and visit as random factors. Technically, the CV is estimated as $100 \times$ standard deviation applying the random effects ANOVA on ln-transformed values. The resulting pooled repeatability is hereby estimated taking in account conditions of variability over sites and operators.

The *success rates* (proportion of patients with successful measurement within FAS) will be reported. The number of attempts necessary to obtain 2 valid replicate measurements will be tabulated in contingency tables by visit.

9. COMPLIANCE WITH GOOD CLINICAL PRACTICES (GCP), ETHICAL CONSIDERATIONS, AND ADMINISTRATIVE ISSUES

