Study Endpoints	
Primary Endpoint: The primary analysis variable will be the percent change of the fractional exhaled nitric oxide (FeNO) measurement made at Visit #1 compared to Visit #2 using the Vivatmo pro™. The first valid FeNO measurement made at each visit will be used for this comparison analysis.
 
Secondary Outcome Measures:
 
 • The change in standard outcome measures (asthma symptoms and spirometry) between Visit #1 to Visit #2 • Repeatability as assessed by replicate FeNO measurements (N=2) at one or more visits. The first two valid FeNO measurements made for each subject at each visit will be used for this repeatability analysis. • Success rate (proportion of patients with successful measurement)
Subject Inclusion / Exclusion Criteria	
See criteria starting on page 23.

Study Procedures	
 Patients meeting study inclusion/exclusion criteria will be consented and will be enrolled in the study. Subjects will be observed during each of two study visits according to routine clinical diagnosis and treatment standards for uncontrolled asthma patients and will have asthma symptoms recorded using a standardized Asthma Control Questionnaire (ACQ). Subjects will have fractional exhaled nitric oxide (FeNO) and spirometry measured and documented at each visit. All study subjects will be asked to perform two valid fractional exhaled nitric oxide (FeNO) measurements at each study visit using the Vivatmo proTM with a limit of 10 total exhalation attempts per subject per visit. If only one valid measurement is taken, it will be used for comparative analysis. No repeatability data will be available for this subject. One operator will guide each subject through the fractional exhaled nitric oxide (FeNO) measurements at each visit. At the first visit, after all study assessments (FeNO, Spirometry, ACQ), subjects will receive therapy by prescription of inhaled corticosteroid (ICS) medication according to routine treatment standards. Subjects will return after 2 weeks (14 days) of treatment for a repeat of measurements.

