Statistical Analysis	
Analysis Population:
 
The Full Analysis Set (FAS) will be defined as all patients intended to receive a FeNO measurement.
 
The Per Protocol Set will be defined as enrolled subjects without major protocol violations, with inhaled corticosteroid (ICS) treatment, and successfully completing at least one valid FeNO measurement at both Visit #1 and Visit #2 will be evaluated for the primary endpoint.
 
Definition of Measured Value:
 
For primary endpoint analysis the value of FeNO measurement will be derived as the result of the first valid measurement.
 
For repeatability, the first and second valid FeNO measurements at each visit will be used. Repeatability will be the pooled result of pairwise analyses for repeatability to demonstrate precision (see below).
 
Descriptive Statistics:
 
Baseline characteristics, such as demographics, as well as analytical clinical data by visit will be summarized using descriptive statistical methods.
 
Continuous data will be summarized using the mean, the median, standard

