	
deviation, and range (minimum and maximum value). Categorical values will be summarized using frequency counts and percentages.
 
Analysis of Primary Endpoint: The change of FeNO values will be estimated in ANOVA with baseline values as the covariate and will be reported as percent change together with the 95%-confidence interval. In a sensitivity analysis, the first valid single measurement is used for the analysis.
 
Analysis of Secondary Endpoints: The relationship between changes in FeNO-values and clinical assessments (spirometry, ACQ-questionnaire) will be assessed by Spearman's rank correlation.
 
Repeatability: Repeatability will be estimated together with the 95%-confidence interval as pooled standard deviation (mean < 50 ppb) and CV (mean ≥ 50 ppb), respectively, using the residual variance component resulting from a random effects ANOVA (as used in CLSI EP05 guideline) with patient and visit as random factors.
 
The resulting pooled repeatabilities are hereby estimated taking into account conditions of variability over sites and operators.
 
Success rates: The success rates (proportion of patients with successful measurement within FAS) will be reported. The number of attempts necessary to obtain 2 valid replicate measurements will be tabulated in contingency tables by visit.
 
Sample Size: Since the effect size of the change (mean change / standard deviation) is on the order of 1 (resulting in N=10 and 13 for power = 80% and 90%, respectively) and therefore large, the sample size is not determined by the primary objective but by the necessity to achieve representative data of FeNO measurement data over all age groups, measurement ranges ($<$, \geq cut off) and sites. Thus, 120 subjects will be recruited.

--	--

TABLE OF CONTENTS

PROTOCOL REVISION HISTORY	3
PROTOCOL APPROVAL	3
PROTOCOL SIGNATURE PAGE	4
LIST OF ABBREVIATIONS	5
STUDY SYNOPSIS	6
TABLE OF CONTENTS	10
1. BACKGROUND AND INVESTIGATIONAL DEVICE	13
1.1. Background	13
1.2. Description of the Device	13
1.3. Intended Use	15
1.4. Special Conditions for Use Statement	16
1.5. Investigator Requirements	16
2. STUDY OBJECTIVES	16
2.1. Primary Objective	16
2.2. Secondary Objectives	17
3. STUDY DESIGN	17
3.1. General Design	17
3.2. Study Endpoints	17
3.3. Number of Subjects	18
3.4. Number of Study Sites	18

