2.2. Secondary Objectives

- To compare changes according to the primary objective with those of spirometry (lung function), and asthma symptoms before and after treatment.
- To evaluate the precision within a series of repeat measurements made for each subject at a single visit.
- To evaluate the success rate of the subject using the device.

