3.2. Study Endpoints

Primary Endpoint

The primary analysis variable will be the percent change of the fractional exhaled nitric oxide (FeNO) measurement made at Visit #1 compared to Visit #2 using the Vivatmo *pro*TM. The first valid FeNO measurement made at each visit will be used for this comparison analysis.

Secondary Outcome Measures:

- The change in standard outcome measures (asthma symptoms and spirometry) between Visit #1 to Visit #2
- Repeatability as assessed by replicate FeNO measurements (N=2) at one or more visits. The first two valid FeNO measurements made for each subject at each visit will be used for this repeatability analysis.
- Success rate (proportion of patients with successful measurement)

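### Does leaving the patient/visit structure of the repeatability ANOVA unstated put the precision estimate at risk?

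*Combined protocol and SAP*

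**What the plan says.** Section 8.4 reports repeatability as a pooled SD where the mean of the measurement pair is below 50 ppb, and as a CV (from ln values) where it is 50 ppb or more. Both are obtained "using the residual variance component resulting from a random effects ANOVA (as used in CLSI EP05 guideline) with patient and visit as random factors". The synopsis describes the model in the same words.

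Other places define what is being estimated:

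- Synopsis, Definition of Measured Value: "Repeatability will be the pooled result of pairwise analyses for repeatability to demonstrate precision". The sentence ends with a pointer to the text below, where the ANOVA is described.
- Section 2.2: "To evaluate the precision within a series of repeat measurements made for each subject at a single visit".
- Section 3.2: "The first two valid FeNO measurements made for each subject at each visit will be used for this repeatability analysis".
- Synopsis, Study Procedures: "One operator will guide each subject through the fractional exhaled nitric oxide (FeNO) measurements at each visit".

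Section 8.4 adds: "The resulting pooled repeatability is hereby estimated taking in account conditions of variability over sites and operators". The only information on how much patients differ in their change is in the synopsis under Sample Size: "Since the effect size of the change (mean change / standard deviation) is on the order of 1".

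**The concern.** Taken alone, the phrase "with patient and visit as random factors" fits more than one model. If visit is nested in patient, every patient-visit cell has its own level and the residual is the difference between the two readings of a pair. If patient and visit are crossed main effects only, visit removes just the average shift from Visit #1 to Visit #2, and each patient's departure from that average falls into the residual.

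That would matter here because treatment begins between the visits, and an effect size near 1 means the SD of the change is about as large as its mean. The additive residual would then mix variation in treatment response with measurement error, and the device would look less precise than it is. The same data could give two clearly different precision figures, depending on how one sentence is coded.

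**Working it through.** **1. The plan's own figure.** The synopsis gives N = 10 and 13 for 80% and 90% power at effect size 1. A paired t-test (noncentral t) gives power 0.803 at n = 10 and 0.911 at n = 13. Two-sided alpha 0.05 is assumed, since the plan states none. Both figures reproduce, which supports reading the effect size as mean paired change divided by its SD.

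**2. Expected mean squares.** Take n patients, 2 visits and 2 readings per visit. Let σe² be the within-pair variance and σpv² the patient-by-visit variance, so Var(true change) = 2σpv².

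- Within cells: 2n df, expectation σe².
- Patient-by-visit: n − 1 df, expectation σe² + 2σpv².

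With visit nested, or crossed with a patient-by-visit term, the residual is the first line alone: σe² on 2 × 120 = 240 df. The additive crossed fit pools both lines:

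[2nσe² + (n − 1)(σe² + 2σpv²)] / (3n − 1) = σe² + [(n − 1)/(3n − 1)] × Var(true change)

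This has 3 × 120 − 1 = 359 df and weight 119/359 = 0.3315, about one third.

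**3. Size of the additive error, balanced data without the 50 ppb split.** The plan gives no device CV and no expected fall, so these are assumed. With true CV 5% and SD of true ln change 0.35: 0.0025 + 0.3315 × 0.1225 = 0.0431, square root 0.208, so 20.8%.

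Now put effect size 1 on the ln scale. The SD of observed change is |ln(1 − fall)|, and the variance of true change is its square minus 2 × 0.05².

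| Assumed fall | SD of ln change | Additive CV | Nested CV |
|---|---|---|---|
| 20% | 0.223 | 13.2% | 5% |
| 30% | 0.357 | 20.7% | 5% |
| 40% | 0.511 | 29.6% | 5% |

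**4. With the planned split at 50 ppb.** Simulation of 120 patients, with values limited to 5–300 ppb. Assumed: between-patient ln SD 0.7, within-pair SD 3 ppb where the true level is below 50 ppb, and CV 8% at or above it.

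| Fall | Baseline geometric mean | SD, additive / nested (ppb) | CV, additive / nested (%) |
|---|---|---|---|
| 20% | 30 ppb | 3.94 / 2.95 | 11.68 / 7.77 |
| 20% | 45 ppb | 4.16 / 3.02 | 12.34 / 8.01 |
| 35% | 30 ppb | 5.42 / 2.90 | 16.35 / 7.98 |
| 35% | 45 ppb | 5.65 / 2.96 | 18.59 / 7.95 |
| 50% | 30 ppb | 6.64 / 2.79 | 20.27 / 7.79 |
| 50% | 45 ppb | 6.65 / 2.87 | 23.37 / 8.09 |

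Inflation runs from 3.94/2.95 = 1.3 to 23.37/8.09 = 2.9. Crossed factors plus a patient-by-visit term gave the same result as nesting in every row.

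**5. Which model the plan calls for.**

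- The synopsis describes a pooling of pairwise analyses and points forward to the ANOVA as the way to do it. An additive residual is not a pooling of pairs.
- The objective is precision at one visit. The additive residual includes disagreement between visits.
- Section 8.4 assigns each measurement pair, not each patient, to the SD or CV stratum. A patient's two visits can fall in different strata, so the unit of analysis is the patient-visit pair.
- A crossed visit factor would have two levels, before and after treatment, which are hardly a random sample of visits. Nested in patient, visit has 120 × 2 = 240 levels, and calling it random makes sense.

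The EP05 citation is given no weight here, because the documents do not reproduce its model.

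**The case for a change.** The best case for a change is that the programmer codes from the model sentence, and that sentence leaves the structure open. The result is meant to demonstrate precision, one added phrase would settle it, and the additive reading can more than triple the figure: with a 40 ppb baseline, a 30% fall and the split applied, a true CV of 5% comes out at 15.9%. Whatever the assumed inputs, any variation in individual response inflates the additive residual.

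The gap and the algebra stand. What does not stand is the step from an unwritten detail to an unsound analysis. Every figure above is conditional on a reading that conflicts with the stated objective, the pairwise description and the pair-based split. Nesting is also not the only safe coding, since a patient-by-visit term reaches the same residual on the same degrees of freedom. An additive fit would have to be chosen against the surrounding text.

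The remark on sites and operators could be read as claiming that the residual contains operator and site variance. It cannot, because one operator guides both readings of a pair. But the sentence describes a pooled figure and can fairly be taken as pooled across sites and operators. Rewording it would alter no result.

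**Conclusion.** No change to the plan follows. The patient/visit structure is a missing detail that an analyst working to the plan's own target fills correctly, by nesting or by a patient-by-visit term, and either returns the within-pair variance (240 df at 120 complete patients, before the split).

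The inflation of about 1.3 to 2.9 times with the split, and the 20.8% in the balanced example, belong only to the additive fit. They rest on assumed falls, baseline levels and device error, and on placing the plan's effect size on the ln scale. The plan states none of these.

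Even if the additive fit were used, the error would overstate imprecision in a secondary endpoint that has no stated acceptance limit. It could not produce a false claim of good precision, and the primary endpoint would not be affected.

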3.3. Number of Subjects

The study is designed to enroll patients that have clinically diagnosed signs and symptoms of uncontrolled asthma and who are candidates for inhaled corticosteroid (ICS) treatment. The study will enroll 120 male and female asthma subjects from 7 to 80 years of age. This will include a target of 40 pediatric subjects (approximately 30% of enrollment) from 7 to 17 years of age and a target of 80 adult subjects (approximately 70% of enrollment) from 18 to 80 years of age. This is estimated to be a sample size sufficient to demonstrate device performance in the intended use population of pediatric and adult patients.. The Sponsor may extend the overall enrollment goal and/or suspend enrollment of adult subjects in order to reach a minimum required number of enrolled pediatric subjects.

It is the goal of the study to include moderate to severe asthma patients to the maximum extent possible and as per the professional discretion of participating physician investigators.

Enrollment should optimally include newly diagnosed asthma patients, but may also include those patients with a previous history or diagnosis of uncontrolled asthma who have not been using corticosteroids for at least 4 weeks prior to study Visit #1. Patients currently using a short-acting inhaled bronchodilator medication (also known as a “rescue inhaler”) or leukotriene modifiers may be enrolled, but should not participate if they have used these medications within one hour of either study Visit #1 or study Visit #2 Vivatmo *pro*TM readings. Patients using inhaled corticosteroids, oral corticosteroids, or who are taking biologic immunotherapy medications should not be enrolled.

Measured FeNO levels from the subject population are expected to encompass the full Vivatmo *pro*TM measurement range from 5 ppb to 300 ppb. If a maximum range measurement goal of 270 ppb is not met by enrollment of 120 subjects then additional subjects may be enrolled until the maximum range measurement goal is met.

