6.2. Study Visit #1 Overview

Study Visit #1 will include patient screening, consent, enrollment, assignment of a Study Subject ID number, subject training on use of the Vivatmo *pro*TM, Vivatmo *pro*TM measurement, spirometry, ACQ assessment, and Case Report Form (CRF) completion.

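### Does the undefined visit and denominator of the success rate let missed second visits count as device failures, or hide real ones?

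*Combined protocol and SAP*

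**What the plan says.** The secondary objective in section 2.2 is "To evaluate the success rate of the subject using the device". Section 3.2 lists the endpoint as "Success rate (proportion of patients with successful measurement", with no visit named. Section 8.4 adds the denominator: "proportion of patients with successful measurement within FAS) will be reported". Section 8.1 defines that denominator: "The Full Analysis Set (FAS) will be defined as all patients intended to receive a FeNO measurement". It is tied neither to a visit nor to attendance.

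The next sentence of section 8.4 reads: "The number of attempts necessary to obtain 2 valid replicate measurements will be tabulated in contingency tables by visit". In both the synopsis and section 8.4 the success rates are in the plural. Section 8.2 also plans descriptive summaries of the analytical clinical data by visit.

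Two other passages mention valid readings without defining the endpoint. The Per Protocol Set in section 8.1 requires "successfully completing at least one valid FeNO measurement at both Visit #1 and Visit #2". The synopsis says that a lone valid reading still enters the comparative analysis. On attempts, the synopsis and sections 3.5, 6.6 and 6.7 allow ten exhalations per visit. Section 6.7 also asks for each valid reading within five attempts, and writes the total as 2 x 5.

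**The concern.** Read as a single per-patient proportion, the definition has two awkward outcomes.

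- **Both visits required, or Visit 2 alone over the Full Analysis Set.** Someone who does not come back is scored as a failure without having used the device that day. So is someone who comes back but is not tested under section 3.3, where users of rescue inhalers or leukotriene modifiers "should not participate if they have used these medications within one hour of either study Visit #1 or study Visit #2". The rate cannot exceed the share tested at Visit 2.
- **Either visit enough.** A subject who succeeds at Visit 1 and fails at Visit 2 counts as a success, so the rate flatters the device.

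Only Visit 1 avoids both outcomes, because "Study Visit #1 will include patient screening, consent, enrollment" and the first measurement fall on the same day. The criterion is open as well: one valid reading or two. In an open-label single-cohort study, a choice among these rules could be made after the data are seen. The stake is the credibility of one stated secondary objective.

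**Working it through.** **The plan's own figures.** None exists for the success rate: no target, precision or attendance is given. The only calculated figures are N = 10 and 13 for the primary change at effect size 1. A two-sided paired t-test at an assumed alpha of 0.05 reproduces them (power 0.803 and 0.911), but they do not bear on this point. The inputs below are therefore assumptions, apart from N = 120 and the ten-attempt limit.

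**1. Spread between rules.** Let s be the success probability per visit and m the share missing Visit 2, with visits independent. Take s = 0.95 and m = 0.10.

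| Rule | Formula | Result |
|---|---|---|
| Both visits, full set | s²(1 − m) = 0.9025 × 0.90 | 81.2% |
| Visit 2, full set | s(1 − m) = 0.95 × 0.90 | 85.5% |
| Either visit | 1 − (1 − s)(1 − s(1 − m)) = 1 − 0.05 × 0.145 | 99.3% |
| Each visit, among those tested | s | 95.0% |

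If each subject's result is the same at both visits, the both-visits rate is 85.5% and the either-visit rate 95.0%. The inflation of the latter disappears.

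**2. The non-attendance gap.** Let p be the validity of one attempt, q = 1 − p, and a the share tested at Visit 2. Within ten independent attempts:

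- at least one valid = 1 − q¹⁰
- at least two valid = 1 − q¹⁰ − 10pq⁹

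At p = 0.7 these are 0.99999 and 0.99986. The two-valid, both-visits rate a × 0.99986² is then 98.0%, 95.0%, 90.0% and 85.0% for a = 0.98, 0.95, 0.90 and 0.85. The 2 to 15 point shortfall is simply 1 − a, or 2.4 to 18 of 120 subjects. It restates the assumed attendance.

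**3. The masking gap.** At p = 0.3 and a = 0.95, with x the per-visit rate, the either-visit rate is x + (1 − x)ax. The criterion must be the same on both sides of the comparison.

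| Criterion | One visit | Either visit | Gap |
|---|---|---|---|
| One valid reading | 97.2% | 99.8% | 2.6 points |
| Two valid readings | 85.1% | 97.1% | 12.0 points |

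Setting 99.8% against 85.1% would mix the two criteria. These figures also treat attempts as independent, although ability belongs to the subject. If p varies between subjects (Beta, mean 0.3, SD 0.2), the either-visit rate is 91.9% for one valid reading and 77.9% for two. The single-visit rates are then 84.1% and 67.1%. Some masking remains (7.8 and 10.8 points), but the rate is no longer near 100%.

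**4. Reporting by visit.** Assume 114 successes among 120 at Visit 1, 12 subjects missing Visit 2, and 103 successes among the 108 tested there.

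- Visit 1: 114/120 = 95.0% (95% CI 89.5 to 97.7)
- Visit 2, tested: 103/108 = 95.4% (89.6 to 98.0)
- Visit 2, full set: 103/120 = 85.8% (78.5 to 91.0)

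Printed with their denominators, the last two lines show that the drop is attendance.

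**5. Five or ten attempts.** Requiring each of two readings within its own five attempts gives (1 − q⁵)². This is 99.5% at p = 0.7 and 93.8% at p = 0.5, against 99.99% and 98.9% on the ten-attempt total: gaps of 0.5 and 5.1 points. The ten-attempt total appears in four places, including section 6.7 itself, so it is the natural basis for scoring.

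**The case for a change.** The case for a change is that the endpoint is a stated secondary objective and its definition really is incomplete. No section names the visit, the criterion or the treatment of an untested Visit 2. Adding by visit would not settle it either, because a Visit 2 rate over the full set still scores non-attenders as failures. The attempts table lists no category for subjects who never reach two valid readings or were not tested. New wording would be cheap and would need no new data.

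The incompleteness stands. The harm does not follow from it, because it needs an analyst to adopt an unfavourable rule that the plan never states, and to report it without the table that section 8.4 requires. That table shows how many subjects reached two valid readings at each visit, so Visit 2 shortfalls stay visible under any headline. It names no categories, but it also excludes none. The two apparent anchors for success do not conflict: one sets eligibility for the primary analysis, and the other describes a table.

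Making Visit 1 with two valid readings the headline is a preference. One valid reading is equally defensible, since the synopsis accepts it for the main comparison. A Visit 2 rate among those tested has its own selection problem: it describes returning, practised users, and subjects who struggled at Visit 1 may be less likely to return.

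**Conclusion.** No change is needed. The visit, criterion and denominator of the success rate are left open, but this is missing detail on a descriptive endpoint with no threshold, hypothesis test or sample-size role. The natural reading is rates by visit with their denominators shown. On the illustrative counts these are 95.0% and 95.4%. The 81% to 99% range arises only under extreme rules that the documents do not state, and on assumed success, attendance and independence; the plan gives none of these.

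Whichever rule is used, the case report forms for each visit (section 7.2) and the device export (section 7.3) let the others be computed. The one-reading and two-reading versions can be shown together, with untested subjects listed. The primary analysis is unaffected. The conclusion would differ if a performance claim or acceptance limit rested on the success rate, but the documents set none.
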